1.1 Background

Lateral patient transfer (lateral transfer) is the act of moving a patient from one horizontal surface to another. Lateral transfer is needed for many reasons, including but not limited to admitting patients from a gurney to hospital stretcher, within hospitals for changing units and when going for imaging, surgery, or testing. Lateral transfers are the most common type of patient transfer, Occupational Safety and Health Administration (OSHA) mandates no more than 35 lbs. be lifted by an individual clinician, yet the average patient weight is nearly 200 lbs., meaning an average patient requires six clinicians to be moved per OSHA mandate. Customer discovery sessions found in typical acute care settings it takes 4-minutes on average to recruit each staff member for lateral transfers creating a 22-minute average time when following this OSHA mandate. As 22-minutes is unreasonable to do a transfer, clinicians are currently forced to ignore mandates to stay on schedule, resulting in 12,000 injuries to U.S. clinicians annually. Typically, overexertion injuries to backs, necks, shoulders, wrists, or elbows are not easily remedied; many of these injuries cause lifelong issues. While there are products available to support lateral transfers, these products have the same problem; they require a separate product to be placed underneath the patient to facilitate the transfer. To get patients on these transferrable surfaces an entirely manual process referred to commonly as “log-rolling” must be performed. This manipulation is attributable to up to 50% of injuries related to lateral transfer. Even with these products available, nurses sustain more injuries than any other profession in any other industry and patient transfer, specifically lateral transfer is a major contributor. When nurses sustain these injuries, it makes them vulnerable to further injury, sometimes unable to participate in transfers post-injury. This creates additional burden and increased risk to uninjured staff as they are held accountable to do the same transfers without support from injured staff. Nurses are in high demand and short supply, as the population ages and patient weight increases, supporting a safe work environment for clinicians is critical.

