1.4.2 Anticipated Risks

SimPull is a standalone lateral patient transfer device, that is not yet approved for market, making it an investigational use device. SimPull is meant to be used in many environments, meaning that in interacting with products that are not specifically made to be compatible with SimPull could result in some risk. Specifically, SimPull attaches to sheets under patients, if the sheets are not positioned well, the patient could turn during transfer. SimPull engages to the surfaces that the patient is being transferred to and from, if any surface is not in the braked or locked position there may be risk to the transfer. These risks are mitigated through sensors that prevent transfer if positioning is jeopardized. The last risk is that the device pulls the patient across one surface to another, in doing so there is some friction, though it has been intentionally reduced as much as possible, this friction could result in risk to the patient.

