3.2 Primary Study Endpoints

Endpoint 1: Difference between transfer methods in time for transfer.

Endpoint 2: Difference between transfer methods in number of staff involved in transfer.

Endpoint 3: Difference between transfer methods in proportion of transfers following the OSHA mandate of no more than 35 lbs. lifted per staff member (lbs. lifter per staff member calculated as: weight of patient in lbs. divided by number of staff involved in transfer).

Endpoint 4: Paired difference in satisfaction scores (satisfaction with current transfer method and with SimPull) on staff questionnaires.

Endpoint 5: Paired difference in self-rated risk of injury (with current transfer method and with SimPull) on staff questionnaires.

4 Subject Selection, Enrollment and Withdrawal

Patient selection will be based on set inclusion and exclusion criteria of patients scheduled for procedures in the cardiac catheterization and electrophysiology procedural area. If the patient meets eligibility requirements, consent will be obtained using a written consent process. **The Principal Investigator and Co-Principal Investigator or study members** with recorded conflict of interest do not have consenting privileges and will not participate in the recruitment or consenting process. Using REDCap, the study team will enter data based off transfer observations. If patient consents and no IRB approved study member is available to perform the transfer, the patient will be excluded from the study. If the patient meets inclusion criteria, the clinical research coordinator will validate that a study member is present to transfer the patient prior to consent,. Enrollment will begin with the first 50 patients using the current method of transfer-followed by the pre-survey of staff. Staff will then receive training on the SimPull transfer device and the next enrolled 50 patients will be transferred with SimPull; followed by post-survey of staff. Study members are defined as employees (registered nurses and technicians) of Mayo Clinic assigned to the cardiac catheterization and electrophysiology procedural areas.

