6.2 Statistical Methods

Descriptive Statistics

Patient and transfer characteristics will be descriptively summarized by transfer type. Staff questionnaires will be descriptively summarized. The difference between transfer methods in time for transfer and number of staff involved in transfer will be tested using two-sample t-tests. A possible secondary analysis would test differences using a regression model adjusting for differences in patient or transfer characteristics. The difference between transfer methods in proportion of transfers following the OSHA mandate of no more than 35 lbs. lifted per staff member will be tested using a Chi-square or Fisher's exact test. A possible secondary analysis would test differences using a regression model adjusting for differences in patient characteristics. The paired differences in mean staff satisfaction scores and self-rated risk of injury scores will be tested using paired tests.

Primary Hypothesis:

SimPull lateral transfer device is a more efficient and safe method of lateral patient transfer than current methods of lateral transfer.

By recording patient weight and the number of clinicians engaged during manual transfers we can calculate the force needed by each individual. Example: Patient weight: 265 lbs., five clinicians: 53 lbs. per clinician (51% higher than the 35 lb. OSHA mandate). This data collection allows risk assessment of clinician injury during transfer in each location by

establishing weight pulled by clinicians and the number of transfers per day. Using this we can also forecast force required and risk of injury over time. Time to complete in seconds will be recorded for each lateral transfer.

Secondary Hypothesis:

Use of the SimPull device for lateral transfers will increase staff satisfaction and be a preferred method of lateral patient transfer.

Data collected pre and post SimPull implementation

- Employee Satisfaction
- Employee Perception of Injury Risk

Staff/Clinician Participant Survey:

Part 1 of Survey – Pre-Training

1. What is your preferred method for performing lateral patient transfers?
 - a. Manual, Assisted, Ceiling Lift, or Air Mattress
2. Do you feel at risk of injury performing lateral patient transfers?
 - a. No Risk, Minimal Risk, Neutral, Some Risk, High Risk
3. How likely do you feel you are to be injured during lateral patient transfer?
 - a. Not at all likely, Not Likely, Neutral, Likely, Very Likely

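### Section 6.2 treats patient weight per clinician as the force each clinician exerts; it is a staffing-to-weight ratio and cannot support force or injury-risk conclusions

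*Combined protocol and SAP*

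**What the plan says.** Under the Primary Hypothesis in Section 6.2, which covers both efficiency and safety, the plan states: "By recording patient weight and the number of clinicians engaged during manual transfers we can calculate the force needed by each individual". Its illustration is "Example: Patient weight: 265 lbs., five clinicians: 53 lbs. per clinician (51% higher than the 35 lb. OSHA mandate". The next sentence says that the data allow an assessment of clinician injury risk by "establishing weight pulled by clinicians and the number of transfers per day", and the one after adds: "Using this we can also forecast force required and risk of injury over time".

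The same quotient appears in Section 3.2. Endpoint 3 compares the two transfer methods on the "proportion of transfers following the OSHA mandate of no more than 35 lbs. lifted per staff member", with the load defined as "weight of patient in lbs. divided by number of staff involved in transfer". Section 1.1 words the threshold as a lifting limit: it "mandates no more than 35 lbs. be lifted by an individual clinician".

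Section 1.1 defines a lateral transfer as movement between two horizontal surfaces. Section 1.4.2 says of SimPull that "the device pulls the patient across one surface to another, in doing so there is some friction". Sections 1.2 and 5.1 say that the device carries almost all of the patient's weight.

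**The concern.** One quotient carries three meanings: pounds lifted (Section 3.2), force needed per person, and weight pulled (both Section 6.2). These are different physical quantities. Patient weight and head count give a ratio of weight to staff. They do not give a force unless something is known about friction and about how the effort is shared.

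The items that Section 6.2 says will be recorded for a transfer are patient weight, number of clinicians and time in seconds. No pull-force measurement, friction or surface variable, or split of effort is named anywhere in the plan. A report that followed Section 6.2 could therefore state forces per clinician, a percentage excess over 35 lb and a forecast of injury risk, none of which the data can support. These statements would sit under the safety half of the primary hypothesis.

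**Working it through.** **1. Reproduce the plan's figure.** Inputs from Section 6.2: weight 265 lb, five clinicians, threshold 35 lb.
- Share per clinician = 265 / 5 = 53 lb.
- Excess = 53 / 35 − 1 = 0.514, or 51%.

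The arithmetic is correct. The question is what the 53 lb represents.

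**2. What a level pull would require.** For a steady slide on level surfaces, with staff as the only source of force, total pull = μ × W, where μ is the friction coefficient and W the patient weight. The mean over n staff is μ × W / n. This equals W / n only when μ = 1.

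The documents give no value for μ. The range below is an assumption, used only to show how much depends on it. The third column assumes that two of the five staff do all the pulling and share it equally.

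| Assumed μ | Mean over 5 staff, μ × 265 / 5 | Each of 2 pulling, μ × 265 / 2 |
|---|---|---|
| 0.2 | 10.6 lb | 26.5 lb |
| 0.4 | 21.2 lb | 53.0 lb |
| 0.6 | 31.8 lb | 79.5 lb |
| 0.8 | 42.4 lb | 106.0 lb |
| 1.0 | 53.0 lb | 132.5 lb |

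The plan reports 53 lb in every row. The mean over five staff is lower whenever μ is below 1. The load on a person who actually pulls exceeds 53 lb once μ passes 53 × 2 / 265 = 0.40 with two pulling, or 53 × 3 / 265 = 0.60 with three pulling. So the size of the error is open, and for an individual clinician its direction is open too.

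These pulls should not be compared with 35 lb, because the plan words that limit as pounds lifted.

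**3. What the quotient does measure.** Section 1.1 already uses it as a staffing rule: a patient of about 200 lb needs 200 / 35 = 5.7, rounded up to six clinicians. That reading needs no physics and is the one the data support.

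**4. Endpoint 3, where the quotient enters a test.** Section 6.1 assumes means of 5 staff under the current method and 2 with SimPull. The heaviest patient who scores compliant is 35 × n:
- Current method: 35 × 5 = 175 lb.
- SimPull: 35 × 2 = 70 lb.

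A 200 lb patient scores 200 / 5 = 40 lb per person under the current method and 200 / 2 = 100 lb per person under SimPull, although the device is said to carry nearly all of the weight. Under SimPull the quotient therefore cannot be read as load per person.

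**The case against.** The strongest defence is that no endpoint is a force. The planned tests cover transfer time, staff number, the 35 lb proportion, satisfaction and self-rated risk. Endpoint 3 states its formula openly. The force and forecast sentences in Section 6.2 say what could be done and commit to no analysis. All of this stands: correcting the label changes no planned test. It does not remove the point, because those sentences sit under the primary hypothesis and tell the authors what they may conclude about injury risk.

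A reader might also infer something stronger: that the rule overstates the load under current methods and so favours SimPull. The documents do not support that, for three reasons:
- They give neither a friction value nor a split of effort. With unequal pulling, the quotient can understate the load on an individual.
- Current practice is not purely a pull. Section 1.1 describes manual log-rolling to place transfer products, and the staff survey lists ceiling lifts and air mattresses. The sentence on force is limited to manual transfers, which leaves most lift and mattress transfers outside it but not log-rolling. The friction remark in Section 1.4.2 concerns the device.
- The only planned between-method test that uses the quotient is Endpoint 3, which applies it to both methods. At the assumed staffing, it counts against SimPull.

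For the same reasons, no percentage of current-method transfers above or below 35 lb of pull can be put forward.

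**Conclusion.** The point holds as one about labelling and interpretation. Patient weight divided by staff is an equal share of body weight. Calling it force, or forecasting injury risk from it, goes beyond what the planned data can show.

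In the plan's own example, the reported 53 lb could correspond to a mean pull of 10.6 lb at an assumed coefficient of 0.2 or 42.4 lb at 0.8. If effort is uneven, it could also correspond to more than 53 lb for those who pull. These figures rest on level, steady sliding and on coefficients that the documents do not give. They show that the answer is undetermined, not what it is.

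The 70 lb and 175 lb cut-offs in Endpoint 3 need only the plan's formula and its assumed mean staffing. They show that the endpoint is a staffing ratio under both methods and is not a measure of personal load when the device bears the weight. No conclusion about which method the force wording favours is warranted.

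**What to change.** In Section 6.2:
- Replace the three labels (force needed, weight pulled, force required) with *patient weight per staff member*, and state that this is a staffing-to-weight ratio and not a measured force.
- Remove the force and injury-risk forecast and the injury-risk assessment that rests on the quotient. Draw no overexertion conclusion from it.
- Keep the 265 lb example, if at all, as a ratio of 53 lb of patient weight per staff member, without the 51% excess.

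In Section 3.2 and in the report, describe Endpoint 3 as the share of transfers with at most 35 lb of patient weight per staff member. Add that it does not measure load per person in SimPull transfers, and that with two staff any patient over 70 lb scores non-compliant.

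This needs a protocol wording change only, with no new data, patients or tests. The cost to the sponsor is giving up a force-based safety statement.

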4. What type of injury do you think you would have during lateral transfers?
 - a. Open response
5. What preventative measures do you take to avoid injury during lateral transfers?
 - a. Open response
6. Are you satisfied with current lateral patient transfer methods?
 - a. Yes/No

Part 2 of Survey – Post Training

1. What is your preferred method for performing lateral patient transfers?
 - a. Manual, Assisted, Lift, or SimPull
2. Do you feel at risk of injury performing lateral patient transfers using the SimPull?
 - a. No Risk, Minimal Risk, Neutral, Some Risk, High Risk
3. How likely do you feel you are to be injured during lateral patient transfer using SimPull?
 - a. Not at all likely, Not Likely, Neutral, Likely, Very Likely
4. What type of injury do you think you would have during lateral transfer using SimPull?
 - a. Open response
5. What preventative measures do you take to avoid injury during lateral transfers using SimPull?
 - a. Open response
6. Are you satisfied with lateral patient transfer using SimPull?
 - a. Yes/No

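### Endpoint 4 calls for a difference in mean satisfaction scores, but satisfaction is one Yes/No item with no scoring rule, so the data give only a paired difference in proportion satisfied

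*Combined protocol and SAP*

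**What the plan says.** Section 3.2 lists Endpoint 4, under the primary endpoints, as "Paired difference in satisfaction scores (satisfaction with current transfer method and with SimPull) on staff questionnaires". Section 6.2 gives the analysis: "The paired differences in mean staff satisfaction scores and self-rated risk of injury scores will be tested using paired tests". Which paired test is meant is not stated.

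The survey is printed in full in Section 6.2. Each part has one satisfaction item, item 6. Part 1 (before training) asks "Are you satisfied with current lateral patient transfer methods? - a. Yes/No". Part 2 (after training) asks "Are you satisfied with lateral patient transfer using SimPull? - a. Yes/No". No coding or scoring rule for satisfaction appears anywhere. Items 2 and 3, on injury risk, have five ordered answers; those of item 2 are "No Risk, Minimal Risk, Neutral, Some Risk, High Risk".

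The secondary objective (Section 2.2) is about staff satisfaction, and the secondary hypothesis in Section 6.2 is directional: "Use of the SimPull device for lateral transfers will increase staff satisfaction and be a preferred method of lateral patient transfer".

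Section 4 describes one pre-survey of staff after the first 50 patients and one post-survey after the next 50.

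**The concern.** The endpoint and its analysis speak of scores and means, while the instrument records two states. With one Yes/No answer before and one after, a staff member can only gain, lose or stay the same. Someone who is content with current methods and much happier with SimPull counts as unchanged, so only those who answer No at baseline can contribute an increase.

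Item 6 is the only direct measure of satisfaction. Item 1 asks for the preferred method. It is nominal and its options differ between the two parts, so it cannot supply a paired score. If many staff already answer Yes before training, the study could fail to show an increase in satisfaction that did occur. Once the baseline has been collected as Yes/No, the graded information cannot be recovered.

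**Working it through.** **The plan's own figures.** Section 6.1 claims more than 99% power with 50 transfers per method for time and for number of staff. Both claims reproduce.
- Time: noncentrality 4 / (3.5 × √(2/50)) = 4 / 0.7 = 5.71. Power is 0.9999 at a two-sided level of 0.05, and higher at the 0.5 printed there.
- Number of staff: 3 / (0.5 × 0.2) = 30. Power is about 1.

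Neither figure concerns Endpoint 4, for which the documents give no sample size, effect size or power.

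**What a Yes/No item yields.** Code No = 0 and Yes = 1. Let n be the number of staff with both answers, b the number moving from No to Yes, and c the number moving from Yes to No.
- Mean paired difference = (b − c)/n, which is the difference in the proportion satisfied.
- Illustration (assumed n = 30, b = 10, c = 2): (10 − 2)/30 = 0.267. McNemar chi-square = (10 − 2)²/(10 + 2) = 5.33. Exact McNemar p = 0.039.

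So a difference can be computed. It carries no information on how much any one person changed.

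**Ceiling.** If p0 is the baseline proportion Yes, the largest possible gain is 1 − p0: 0.5, 0.3, 0.2 or 0.1 at 50%, 70%, 80% or 90% baseline Yes.

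**Switches needed.** When all m switches go one way, the exact two-sided McNemar p is 2 × 0.5^m.

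| m | p |
|---|---|
| 4 | 0.125 |
| 5 | 0.0625 |
| 6 | 0.031 |

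Six is therefore the minimum for p < 0.05.

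**Best-case power.** Suppose every No becomes Yes and nobody reverts. The number of switches is then Binomial(n, 1 − p0), and power is the probability of six or more. Neither n nor p0 is in the documents, so both are varied as assumptions, as is the 0.05 level.

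| Staff (n) | Baseline Yes (p0) | Power |
|---|---|---|
| 30 | 50% | 1.00 |
| 30 | 70% | 0.92 |
| 30 | 80% | 0.57 |
| 30 | 90% | 0.07 |
| 10 | 80% | 0.01 |
| 20 | 80% | 0.20 |
| 50 | 80% | 0.95 |

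These are upper limits for each setting. If only 80% of the No answers convert and 5% of the Yes answers revert, power with 30 staff is 0.93 at 50% baseline Yes, 0.46 at 70% and 0.15 at 80%.

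**The case against.** A reader might infer that the planned mean difference cannot be derived at all. The documents do not support that: coded 0/1, the mean difference is the paired difference in proportions, a legitimate quantity. A reader might also infer that the plan prescribes the wrong test. Section 6.2 speaks only of paired tests, and McNemar's test is one. What can fairly be said is that the test is unnamed and that the words mean and scores do not fit a binary item.

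The size of the ceiling is also open. With 30 staff and half satisfied at baseline, or 50 staff and 80% satisfied, best-case power is high. A single unfavourable scenario would overstate the case, and the documents do not say where in the range this study lies.

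Survey frequency is not quite settled. Section 3.1 can be read as one survey for each of the 100 transfers. If staff answered repeatedly, a per-person proportion of Yes answers would be a graded score. Against that, Section 4 describes one survey before and one after, the two parts are labelled by their timing relative to training, and no rule for averaging repeated answers is given.

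Finally, Yes/No is a defensible, if coarse, choice for a pilot, and a five-level item has a ceiling too. That ceiling, however, binds only staff already in the top category. The contrast with the risk items should not be pushed far either: they have five levels, but the plan does not say whether item 2, item 3 or a combination forms the Endpoint 5 score.

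**Conclusion.** The mismatch stands. The plan promises a paired difference in mean satisfaction scores, and the printed instrument delivers a paired difference in the proportion satisfied. A graded within-person change cannot be obtained, and staff satisfied at baseline cannot show the increase that the secondary hypothesis predicts.

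The loss ranges from negligible to nearly total: best-case power runs from about 1.00 to 0.07 with 30 staff as baseline Yes goes from 50% to 90%. This rests on one pre-survey and one post-survey per person, on answers that can be linked within person, on a two-sided level of 0.05, and on assumed staff numbers and baseline satisfaction.

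Severity is moderate. Endpoint 4 is listed among the primary endpoints but serves the secondary objective, and the time and staff-number results are unaffected.

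**What to change.** Before the pre-survey, give item 6 in both parts one identical five-level scale (very dissatisfied, dissatisfied, neutral, satisfied, very satisfied), in the style of items 2 and 3. State its coding, and analyse the within-person change with a Wilcoxon signed-rank test. That test also needs at least six non-zero changes when all go one way (2 × 0.5⁶ = 0.031). The gain is that more staff can register a change. The cost is new response options for one item in both parts and one line each in Sections 3.2 and 6.2, with no extra patients, staff or visits.

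If Yes/No stays, or the baseline has already been collected, redefine Endpoint 4 as the paired change in the proportion satisfied, name the exact McNemar test, and remove the words mean and scores for satisfaction. This costs only text, but the ceiling remains and should be acknowledged when the result is reported.

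Either way, state in Sections 3.1 and 4 whether each staff member is surveyed once before and once after, or at each transfer.

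### Endpoints 4 and 5 tie transfer method to survey occasion, because staff rate existing methods only in Part 1 and SimPull only in Part 2; repeating three items in Part 2 would allow a check

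*Combined protocol and SAP*

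**What the plan says.** Section 3.2 lists both staff-survey outcomes among the primary endpoints. Endpoint 4 is the "Paired difference in satisfaction scores (satisfaction with current transfer method and with SimPull) on staff questionnaires" and Endpoint 5 the "Paired difference in self-rated risk of injury (with current transfer method and with SimPull) on staff questionnaires". For the analysis, section 6.2 states: "The paired differences in mean staff satisfaction scores and self-rated risk of injury scores will be tested using paired tests". It does not name the test.

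Section 4 fixes the order: "Enrollment will begin with the first 50 patients using the current method of transfer-followed by the pre-survey of staff". Training comes next, and then "the next enrolled 50 patients will be transferred with SimPull; followed by post-survey of staff".

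The survey is printed in section 6.2. Item 6 of Part 1 (pre-training) is "Are you satisfied with current lateral patient transfer methods", and item 6 of Part 2 (post-training) is "Are you satisfied with lateral patient transfer using SimPull". Both are answered Yes or No. Items 2 and 3, on perceived risk and likelihood of injury, have five levels. In Part 1 they name no method; in Part 2 they name SimPull.

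**The concern.** A paired difference between two methods is meant to remove differences between people. It does not remove a difference between occasions when every person rates one method on the first occasion and the other on the second. Between the surveys, staff receive hands-on training on a device whose stated rationale is preventing clinician injury (sections 1.1, 1.4.1 and 3.1), in a study funded by the company that supplies it (sections 5.6 and 11.1). A general change in how staff answer is therefore plausible, and it would be counted as an effect of SimPull. Staff satisfaction is the secondary objective (section 2.2), and the plan tests it formally rather than only describing it.

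A second, smaller issue is that a paired analysis uses only people with both ratings. The plan gives no rule for a missed survey, no description of how a person's two surveys are linked, and no number of staff.

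**Working it through.** **Step 1: which method is rated on which occasion.**

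| Item | Part 1, pre-training | Part 2, after SimPull transfers |
|---|---|---|
| 2, feeling at risk (five levels) | no method named; the timing implies existing methods | SimPull |
| 3, likelihood of injury (five levels) | no method named; the timing implies existing methods | SimPull |
| 6, satisfaction (Yes/No) | current methods | SimPull |

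The two cells needed to separate method from occasion are missing: the current method in Part 2 and SimPull in Part 1. All staff follow the same order, and section 5.2 states that patients are not randomised to a method. The optional regression models in section 6.2 concern the transfer outcomes (Endpoints 1 to 3), not the surveys.

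**Step 2: what the paired difference estimates.** Let M be the SimPull effect and S the average shift in answers between occasions. The mean of (Part 2 SimPull rating minus Part 1 current-method rating) is M + S. With one rating per person per occasion, M and S cannot be estimated separately.

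**Step 3: illustration for Endpoint 5.** The plan states no power, effect, SD or staff number for Endpoints 4 and 5, so there is no figure to reproduce. All inputs here are assumptions: n staff with complete pairs, M = 0, S = d SDs of the paired differences, and a two-sided paired t-test at 0.05. The rejection probability is P(|T| > t(0.975, n−1)), where T is noncentral t with n−1 degrees of freedom and noncentrality d√n. For n = 30 and d = 0.3, the noncentrality is 0.3 × √30 = 1.643 and the critical value is 2.045.

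| Staff | d = 0.2 | d = 0.3 | d = 0.5 |
|---|---|---|---|
| 20 | 0.136 | 0.247 | 0.565 (0.5645) |
| 30 | 0.185 | 0.355 | 0.754 |
| 40 | 0.235 | 0.457 | 0.869 |

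With no shift, each entry would be 0.05.

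**Step 4: why Step 3 does not cover Endpoint 4.** A paired difference of Yes/No answers is −1, 0 or +1. With mean difference d, its SD cannot exceed √(1 − d²). That is √(1 − 0.09) = 0.954 at d = 0.3 and √(1 − 0.25) = 0.866 at d = 0.5. An SD of 1.0 with either shift is impossible, and a t-test is not the natural test for such an item. Step 2 applies to Endpoint 4; the table does not.

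**Step 5: lost pairs.** Suppose there is one pre-survey and one post-survey per person, and a share m (assumed) misses each survey independently. Then (1 − m)² of the pairs remain: 0.9² = 81%, 0.8² = 64% and 0.7² = 49% for m = 10%, 20% and 30%. Depending on how far the misses overlap, the range runs from 1 − 2m to 1 − m: 80–90%, 60–80% and 40–70%.

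**The case against.** The pre/post structure is an open choice in a small, non-randomised pilot, and every endpoint is confounded with study phase. This point is the survey-level form of that limitation, and added items do not remove it. That stands. It supports calling the change an improvement, not the repair of an error.

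Training is required before anyone may use SimPull, so part of its influence on the SimPull rating arguably belongs to the method. That also stands, but it does not cover a general shift in how risk or satisfaction is judged.

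Part 2 does compare methods on one occasion: item 1 asks for the preferred method, with SimPull among the options, and preference is part of the secondary hypothesis. So it would be wrong to say that Part 2 is silent on other methods. Preference, however, is neither Endpoint 4 nor Endpoint 5.

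A reader might infer that every missed form loses a pair. The documents do not settle this. Section 3.1 can be read as one survey form per transfer, in which case a single missed form need not lose a pair. Section 4 describes one pre-survey and one post-survey. Under either reading, method stays tied to study phase.

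A reader might also conclude that the same-occasion Part 2 contrast should replace the endpoint definition. The documents do not support that. A current-method rating given after SimPull use would be retrospective, unblinded and open to contrast effects, whereas the Part 1 rating precedes SimPull training and use. For the same reason, the Part 1 to Part 2 change in the current-method rating would mix occasion shift with contrast and is not a clean measure of the shift.

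**Conclusion.** The point holds as a limitation of the survey design that can be eased cheaply. As written, the paired tests for Endpoints 4 and 5 estimate the SimPull effect plus any occasion shift, and no planned analysis separates the two. For items 2 and 3 this rests on reading the unnamed method in Part 1 as the existing one, which the pre-training timing makes the only sensible reading.

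The size of the bias cannot be computed from the documents. For the five-level risk items only, and under the assumptions of Step 3, a shift of 0.3 SD would give a significant result with no method effect in about 25%, 36% or 46% of studies with 20, 30 or 40 staff; a shift of 0.5 SD would do so in about 56%, 75% or 87%. A reader might take these as estimates for this trial or extend them to satisfaction; neither is supported. The loss of pairs is conditional on one pre-survey and one post-survey per person.

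**What to change.** 1. In Part 2, repeat items 2, 3 and 6 for the current method, worded in parallel with the SimPull items.
2. Keep the Part 1 versus Part 2 comparison as the definition of Endpoints 4 and 5.
3. Pre-specify the within-person Part 2 contrast (current method versus SimPull) as a supportive sensitivity analysis. Anyone who completes Part 2 then contributes a pair to it, even if Part 1 was missed; someone who misses Part 2 still does not.
4. Report the Part 1 to Part 2 change in the current-method rating as an indicator of occasion shift, not a pure measure of it.
5. Reconcile sections 3.1 and 4 on whether staff complete one form per transfer or one survey per phase, and state how a person's surveys are linked and how a missing one is handled.

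The cost is three survey items and a few sentences in section 6.2. Patient procedures, sample size and timeline are unaffected. The added rating is itself imperfect, for the reasons given under the objection, so it reduces the confounding without removing it. The items must be in place before Part 2 is given, because a same-occasion rating cannot be recovered afterwards.
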